5 TREATMENT PLAN

5.1 Treatment Regimen

This is an open-label, single-arm, phase 2 study of nivolumab given every 14 days intravenously in combination with cabozantinib given orally once daily for 28 days. Up to 35 participants will be enrolled to the study to assess the efficacy of the combination as defined by objective response rate (ORR) according to RECIST 1.1, in patients with carcinoid tumors.

No investigational or commercial agents of therapies other than those described below may be administered with the intent to treat the participant's malignancy.

Regimen Description					
Agent	Premedications; Precautions	Dose	Route	Schedule	Cycle Length
Nivolumab	Not routinely necessary unless prior infusion reaction.	240mg	IV	Every 14 days	28 days (4 weeks)
Cabozantinib	Not necessary	40mg	oral	Continuous, once daily*	

*The participant will be requested to maintain a medication diary of each dose of medication. The medication diary will be returned to clinic staff at the end of each cycle.

5.2 Pre-Treatment Criteria

5.2.1 Cycle 1, Day 1

Participants do not need to re-meet eligibility criteria on Cycle 1, Day 1 if screening laboratory evaluations were completed within 3 days of Cycle 1 Day 1.

- absolute neutrophil count $\geq 1,500/\text{mcL}$
- platelets $\geq 100,000/\text{mcL}$
- hemoglobin $\geq 9 \text{ g/dL}$
- total bilirubin $\leq 1.5 \times$ institutional upper limit of normal (ULN) (or $2.0 \times$ ULN in patients with documented Gilbert's Syndrome)
- AST(SGOT)/ALT(SGPT) $\leq 2.5 \times$ institutional ULN or $\leq 3 \times$ institutional ULN for participants with documented liver metastases
- Creatinine $< 1.5 \times$ within normal institutional ULN OR creatinine clearance $\geq 40 \text{ mL/min}$ (using Cockcroft-Gault formula) for participants with creatinine levels above institutional ULN.
- urine protein/creatinine ratio (UPCR) ≤ 1 .
- Urine pregnancy test in women of child-bearing age

5.2.2 Subsequent Cycles

- absolute neutrophil count $\geq 1,000/\text{mcL}$
- total bilirubin $\leq 1.5 \times$ institutional upper limit of normal (ULN) (or $2.0 \times$ ULN in patients with documented Gilbert's Syndrome)
- AST(SGOT)/ALT(SGPT) $\leq 2.5 \times$ institutional ULN or $\leq 3 \times$ institutional ULN for participants with documented liver metastases
- Urine pregnancy test in women of child-bearing age every 4 weeks (+/- 1 week)

5.3 Agent Administration

On days when Nivolumab and Cabozantinib are administered on the same day (i.e. Day 1 of each cycle) the order of agent administration does not matter.

5.3.1 Nivolumab Administration

Nivolumab is available as 100 mg vials (10 mg/mL), which include an overfill. It is supplied in 10 mL type I flint glass vials with butyl stoppers and aluminum seals. Nivolumab injection can be infused undiluted (10 mg/mL) or diluted with 0.9% Sodium Chloride Injection, USP (USP to a final concentration ranging from 1 mg/mL to 10 mg/mL. The total volume of infusion must not exceed 160 mL.) or 5% Dextrose.

Nivolumab will be administered every 14 days at a dose of 240 mg given intravenously over 30 minutes (+/- 10 minutes) using a volumetric pump with 0.2 to 1.2 micron pore size, low- protein binding polyethersulfone membrane in-line filter. Please refer to the Investigational Brochure for further details regarding storage, preparation and administration. Care must be taken to assure sterility of the prepared solution as the product does not contain any antimicrobial preservative or bacteriostatic agent.

5.3.2 Cabozantinib administration

Cabozantinib will be administered orally, once daily for 28 days at a dose of 40 mg. Cabozantinib should be taken 2 hours after a meal (water is permitted) with a full glass of water (8oz/240mL). Participants should continue to fast for 1 hour after taking cabozantinib. Participants will be provided with dosing instructions, a drug diary and a sufficient supply of cabozantinib for continuous daily dosing. Cabozantinib should be dosed on an outpatient basis even on days where Nivolumab and Cabozantinib are dosed together (i.e. Day 1 of each cycle). While taking Cabozantinib, participants should avoid consumption of grapefruit and Seville oranges. Cabozantinib should not be crushed, chewed, or dissolved in water.

Subjects should be instructed to take their cabozantinib dose at approximately the same time every day. If a subject misses a dose, the dose may be taken later only if it is within 12 hours of when the missed dose should have been taken. The missed dose should not be made up if it is within 12 hours of the next scheduled dose.

Management and dose modifications associated with the above adverse events are outlined in Section 6.

5.4 General Concomitant Medication and Supportive Care Guidelines

5.4.1 Concomitant Medications Guidelines

Medications or vaccinations specifically prohibited in the exclusion criteria are not allowed during the ongoing trial. If there is a clinical indication for one of these or other medications or

vaccinations specifically prohibited during the trial, discontinuation from trial therapy or vaccination may be required. The investigator should discuss any questions regarding this with the overall PI.

Acceptable Concomitant Medications

All treatments that the investigator considers necessary for a subject's welfare may be administered at the discretion of the investigator in keeping with the community standards of medical care and documented in the medical record. Selected medications of interest received within 28 days before the first dose of trial treatment and 30 days after the last dose of trial treatment, including dosage, frequency, route, and dates of administration will be recorded.

Concurrent use of somatostatin analogs is allowed, provided that the patient has been on a stable dose for at least two months.

Concomitant medications that are known to prolong the QTcF interval and should be used with caution in subjects who receive cabozantinib until they have permanently discontinued cabozantinib treatment (refer to <http://www.qtdrugs.org> for a list of drugs which have the potential to prolong the QTcF interval).

Drugs known to be P-glycoprotein substrates (e.g. fexofenadine, aliskiren, ambrisentan, digoxin, colchicine, maraviroc, posaconazole, tolvaptan, etc.) should be used with caution as cabozantinib can cause increased P-glycoprotein substrate plasma concentrations.

MRP2 inhibitors such as cyclosporine, delavirine, efavirenz, and emtricitabine should be used with caution during treatment with cabozantinib as coadministration can cause increased cabozantinib plasma concentrations.

Highly protein-bound medications (e.g. diazepam, furosemide, dicloxacillin, propranolol, etc.) should be used with caution during treatment with cabozantinib.

Bisphosphonates should be used with caution due to the nephrotoxic potential and potential for osteonecrosis of the jaw previously described in association with these agents.

Prohibited Concomitant Medications

Subjects are prohibited from receiving the following therapies during the Screening and Treatment Phase of this trial:

- Antineoplastic systemic chemotherapy or biological therapy
- Immunotherapy not specified in this protocol
- Investigational agents other than nivolumab and cabozantinib
- Radiation therapy
- Live vaccines within 28 days prior to the first dose of trial treatment and while participating in the trial. Examples of live vaccines include, but are not limited to, the following: measles, mumps, rubella, varicella/zoster, yellow fever, rabies, BCG, and typhoid vaccine. The use of the inactivated seasonal influenza vaccine (Fluzones, BCG, and ty)
- Systemic glucocorticoids should be avoided for any purpose other than to modulate symptoms from radiation or an event of clinical interest of suspected immunologic

etiology. If corticosteroids are required for this purpose, the minimum effective dose should be used.

- Full dose oral anticoagulation/antiplatelet therapy is not permitted. Low dose aspirin \leq 81mg/day is allowed. Anticoagulation with therapeutic doses of LMWH is allowed in patients who are on a stable dose of LMWH for at least 6 weeks. Treatment with warfarin is not allowed.
- CYP3A4 Inhibitors

Chronic concomitant treatment with strong inhibitors of CYP3A4 is not allowed during on this trial. The following drugs are EXAMPLES of strong inhibitors of CYP3A4 and are not allowed during treatment with cabozantinib.

- Indinavir
- Clarithromycin
- Ketoconazole

CYP3A4 inhibiting foods such as grapefruit/grapefruit juice and Seville oranges may increase plasma concentrations of cabozantinib and should be avoided during treatment with cabozantinib.

Because lists of these agents are constantly changing, please consult and review any drugs for their potential to inhibit CYP3A4.

- CYP3A4 Inducers

Chronic concomitant treatment with strong inducers of CYP3A4 is not allowed during on this trial. The following drugs are EXAMPLES of strong inducers of CYP3A4 and are not allowed during treatment with cabozantinib

- Rifampin
- Carbamazepine

Because lists of these agents are constantly changing, please consult and review any drugs for their potential to induce CYP3A4.

5.4.2 Supportive Care Guidelines – general medications

Patients should receive full supportive care while on this study.

This includes blood product support, antibiotic treatment, and treatment of other newly diagnosed or concurrent medical conditions. All blood products and concomitant medications such as antidiarrheals, analgesics, and/or antiemetics received from the first day of study treatment administration until 30 days after the final dose must be recorded in the medical records.

Antiemetics may be used at the discretion of the treating physician.

Antiemetic agents, along with supportive care, may be used as clinically appropriate at the first sign of nausea and vomiting. 5-HT3 receptor antagonists are recommended over chronic use of NK-1 receptor antagonists and dexamethasone due to possible CYP3A4 interactions.

Diarrhea management is per the discretion of the treating physician.

Diarrhea may need to be managed conservatively with medications such as loperamide, diphenoxylate/atropine, deodorized tincture of opium, or octreotide as clinically appropriate at the first sign of diarrhea. Treating physicians may wish to instruct patients to notify their physician immediately at the first signs of poorly-formed or loose stool or an increased frequency of bowel movements.

Patients with severe diarrhea may need to be assessed for intravenous hydration, correction of electrolyte imbalances, and dietary adjustments.

Prevention of Skin Toxicity

Patients could be advised to use prophylactic measures for skin care. These measures may include: the use of hypoallergenic moisturizing creams, ointment for dry skin, sunscreen with SPF ≥ 30 ; avoidance of exposure of hands and feet to hot water; protection of pressure-sensitive areas of hands and feet; and use of thick, cotton gloves and socks to prevent injury and to keep the palms and soles dry. Treating physicians may wish to carefully monitor patients with skin disorders for signs of infection (e.g. abscess, cellulitis, or impetigo).

Early signs of hand-foot syndrome can include tingling, numbness, and slight redness or mild hyperkeratosis. Early manifestations include painful, symmetrical, red and swollen areas on the palms and soles. Treating physicians may wish to consider adequate interventions to prevent worsening of skin symptoms such as blisters, desquamations, ulcerations, or necrosis of affected areas, including aggressive management of symptoms and an early dermatology referral.

Recommendations for treatment of palmar-plantar erythrodysesthesia (hand-foot) syndrome include urea 20% cream twice daily and clobetasol 0.05% cream once daily. Analgesics (e.g. NSAID, GABA agonist, narcotic) can be used for pain control if needed.

Prevention of GI Perforation/Fistula and Non-GI Fistula Formation

Treating physicians may wish to consider carefully monitoring patients for episodes of abdominal pain, especially in patients with known risk factors for developing GI perforation/fistula or non-GI fistula, to allow for early diagnosis.

Prevention of Mucositis and Stomatitis

Comprehensive dental examination may be used as a preventative measure to identify any potential complications prior to initiation of protocol therapy, and, if indicated, the appropriate correction may need to be implemented such as modification of ill-fitting dentures and appropriate care of gingivitis. During treatment with cabozantinib, treating physicians may wish to advise patients to maintain good oral hygiene and standard local treatments such as non-traumatic cleansing and oral rinses (e.g. with a weak solution of salt and baking soda), as well as noting that the oral cavity should be rinsed and wiped after meals, and dentures should be cleaned and brushed often to remove plaque.

Prevention of Osteonecrosis of the Jaw (ONJ)

Patients using concomitant antiangiogenic drugs, bisphosphonates, or denosumab may need to be monitored for ONJ more frequently, and treating physicians may wish to advise patients who have previously been treated with or concomitantly receive these medications to avoid invasive dental procedures if possible. In cases where dental procedures are unavoidable, treating physicians may wish to consider the risks and benefits of a dental procedure, the extent of the procedure, as well as the risk of developing osteonecrosis of the jaw when deciding how long to hold protocol therapy.

Growth Factors

Blood products and growth factors should be utilized as clinically warranted and following institutional policies and recommendations.

White Blood Cell Growth Factors and other FDA-approved White Blood Cell Growth Factor biologics may not be used to avoid dose reductions, delays or to allow for dose escalations specified in the protocol.

5.5 Criteria for Taking a Participant Off Protocol Therapy

Duration of therapy will depend on individual response, evidence of disease progression and tolerance. In the absence of treatment delays due to adverse event(s), treatment may continue for indefinite number or until one of the following criteria applies:

1. Disease progression by RECIST 1.1 Criteria
Although the primary endpoint is ORR as defined by RECIST 1.1, patients may remain on protocol therapy until the time of disease progression by irRC criteria. The immune criteria allows treatment beyond initial radiographic worsening of disease in order to distinguish between pseudoprogression and true disease progression.
2. Participants who have attained a confirmed complete response (CR) and who have been treated for at least 24 weeks on protocol therapy and had at least four treatments with nivolumab beyond the date when the initial CR was declared. Participants who stop nivolumab with CR may be eligible for additional nivolumab therapy if they progress after stopping study treatment. This retreatment is termed the Second Course Phase Therapy, as summarized below.
3. Intercurrent illness that prevents further administration of treatment
4. Unacceptable adverse event(s). If the subject does not recover from his or her toxicities to tolerable Grade ≤ 2 within 6 weeks, the subject will have study treatment discontinued unless there is unequivocal evidence that the subject is benefitting. In this situation, a subject may be able to restart therapy with a dose reduction upon resolution of the toxicity and with agreement of the principal investigator / Sponsor.
5. Participant demonstrates an inability or unwillingness to comply with the oral medication regimen and/or documentation requirements. OR Significant noncompliance with the protocol schedule in the opinion of the investigator. OR Subjects who cannot tolerate the minimum protocol-specified dose of study treatment will have study treatment discontinued.
6. Participant decides to withdraw from the protocol therapy
7. General or specific changes in the participant's condition render the participant unacceptable for further treatment in the judgment of the treating investigator

8. Sexually active subjects who refuse to use medically accepted barrier methods of contraception (eg, male condom, female condom) during the course of the study and for 5 months (women) or 7 months (men) after discontinuation of nivolumab and 4 months after discontinuation of cabozantinib
9. Women who become pregnant or are breastfeeding
10. Request by regulatory agencies for termination of treatment of an individual subject or all subjects under the protocol

Participants will be removed from the protocol therapy when any of these criteria apply. The reason for removal from protocol therapy, and the date the participant was removed, must be documented in the case report form (CRF). Alternative care options will be discussed with the participant.

When a participant is removed from protocol therapy and/or is off of the study, the relevant Off-Treatment/Off-Study information will be updated in OnCore.

Second Course Phase (Retreatment Period)

Participants may elect to stop nivolumab and cabozantinib with confirmed CR after at least 24 weeks of treatment.

Subjects who stop nivolumab and cabozantinib with CR may be eligible for additional nivolumab and cabozantinib therapy if they progress after stopping study treatment. This retreatment is termed the Second Course Phase of this study and is only available if the study remains open and the subject meets the following conditions:

- Stopped initial treatment with nivolumab and cabozantinib after attaining an investigator-determined confirmed CR according to RECIST 1.1, was treated for at least 24 weeks with nivolumab before discontinuing therapy, and received at least four treatments with nivolumab beyond the date when the initial CR was declared

AND

- experienced an investigator-determined confirmed radiographic disease progression after stopping their initial treatment with nivolumab
- did not receive any anti-cancer treatment other than cabozantinib since the last dose of nivolumab
- meets all other study inclusion/exclusion criteria, as per Section 3.

Subjects who restart treatment will be retreated at the same dose and dose interval as when they

last received nivolumab. Visit requirements are as outlined for subjects on the initial treatment phase of the trial.

5.6 Duration of Follow Up

Participants will be followed for initiation of a new regimen of anti-neoplastic therapy, first disease progression event after removal from protocol therapy or until death . Tumor assessments should continue to be performed every 12 weeks on these participants until first disease progression event or until death, whichever occurs first.

Participants removed from protocol therapy for unacceptable adverse event(s) will be followed until resolution or stabilization of the adverse event.

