1.3 Secondary Objective(s)

- 1.3.1 To evaluate the safety and tolerability of cabozantinib in combination with nivolumab in patients with advanced carcinoid tumors.
- 1.3.2 To evaluate the ORR of cabozantinib in combination with nivolumab in patients with advanced carcinoid tumors according to immune-related response criteria (irRC).
- 1.3.3 To evaluate the duration of response in patients with advanced carcinoid tumors receiving the combination of cabozantinib and nivolumab.
- 1.3.4 To evaluate progression-free survival of patients with advanced carcinoid tumors treated with the combination of cabozantinib and nivolumab.
- 1.3.5 To evaluate overall survival of patients with advanced carcinoid tumors treated with the combination of cabozantinib and nivolumab.

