5.7 Criteria for Taking a Participant Off Study

Participants will be removed from study when any of the following criteria apply:

- Lost to follow-up
- Withdrawal of consent for data submission
- Death

The reason for taking a participant off study, and the date the participant was removed, must be documented in the case report form (CRF). In addition, the study team will ensure Off Treatment/Off Study information is updated in OnCore in accordance with DF/HCC policy REGIST-101.

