10 STUDY CALENDAR

Baseline evaluations are to be conducted within 2 weeks prior to start of protocol therapy. Scans and x-rays must be done \leq 4 weeks prior to the start of therapy. In the event that the participant's condition is deteriorating, laboratory evaluations should be repeated within 48 hours prior to initiation of the next cycle of therapy.

Assessments must be performed prior to administration of any study agent. Study assessments and agents should be administered within \pm 3 days of the protocol-specified date, unless otherwise noted.

	Screening	Cycle 1		Cycle 2			Cycle 3+		End of Treatment (Within 30 Days of Last Dose)	Safety Follow Up (100 Days After Last Dose) ^c
		Day 1	Day 15	Day 1	Day 15	Day 16- 28 ^j	Day 1	Day 15		
Cabozantinib ^A		X	X	X	X		X	X		
Nivolumab ^B		X	X	X	X		X	X		
Informed consent	X									
Medical history	X									
Concurrent Medications ^l	X									
Physical exam ^d	X	X	X	X	X		X	X	X	X
Vital signs ^e	X	X	X	X	X		X	X	X	X
Performance status	X	X		X			X		X	X
CBC w/diff, plts ^f	X	X	X	X	X		X	X	X	X
Serum chemistry ^a	X	X	X	X	X		X	X	X	X
Urine protein creatinine ratio	X	X		X			X			
TSH/fT4 ^g	X	X		X			X			
Pregnancy Test ^b	X	X ^b		X ^b			X ^b			
Coagulation Panel (PT/PTT)	X									
LDH	X									
EKG	X	X		X			X			
Research Biopsy ^j	X				X					
Research Blood ^k	X			X			X		X	
Research Stool	X ^m				X ⁿ					
Adverse event evaluation		X-----X							X	
Tumor measurements ^b	X	Tumor measurements are repeated every 8 (+/- 1) weeks for the first 24 weeks, then every 12 (+/- 1) weeks thereafter as indicated below. Documentation (radiologic) must be provided for participants removed from study for progressive disease.							X	

	A: Cabozantinib: 40mg PO days 1-28 of a 28 day cycle
	B: Nivolumab: 240 mg IV on days 1, 15 of a 28 day cycle.

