11.1.6 Survival and Time to Progression Definitions

Overall Survival: Overall Survival (OS) is defined as the time from randomization (or registration) to death due to any cause, or censored at date last known alive.

Progression-Free Survival: Progression-Free Survival (PFS) is defined as the time from randomization (or registration) to the earlier of progression or death due to any cause. Participants alive without disease progression are censored at date of last disease evaluation.

Time to Progression: Time to Progression (TTP) is defined as the time from randomization (or registration) to progression, or censored at date of last disease evaluation for those without progression reported.

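### Section 5.6 can be read as ending follow-up at new therapy or progression, no survival contact is scheduled after the 100-day visit, and overall survival would be biased upward if sites work that way

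*Combined protocol and SAP*

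**What the plan says.** Section 1.3.5 sets the objective: "To evaluate overall survival of patients with advanced carcinoid tumors treated with the combination of cabozantinib and nivolumab". Section 11.1.6 gives the definition: "Overall Survival (OS) is defined as the time from randomization (or registration) to death due to any cause, or censored at date last known alive". Section 16.3 estimates OS by Kaplan-Meier and censors patients who are alive at cut-off, or lost, at their last contact.

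On follow-up, Section 5.6 states that participants will be "followed for initiation of a new regimen of anti-neoplastic therapy, first disease progression event after removal from protocol therapy or until death". Its next sentence deals with scans: "Tumor assessments should continue to be performed every 12 weeks on these participants until first disease progression event or until death, whichever occurs first".

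Section 5.7 lists the exits from the study under the words "Participants will be removed from study when any of the following criteria apply". They are loss to follow-up, withdrawal of consent for data submission, and death. Progression and new therapy are not among them.

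Elsewhere progression is treated as an exit. Section 9.2 and calendar footnote k (research blood) refer to patients who go off study for progression or for some other reason. The tumor-measurement row of the Section 10 calendar refers to removal from study for progressive disease. The last calendar column is headed "Safety Follow Up (100 Days After Last Dose"; its footnote calls it an off-study evaluation and gives its purpose as finding serious adverse events.

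**The concern.** Section 5.6 is the only section that sets how long participants are followed. If everyone were followed to death regardless, the first two events in its list would do nothing as limits on duration, so a site could reasonably read the list as end points of follow-up. The wording in 9.2 and 10 supports that reading, and no section schedules a vital-status contact after the 100-day visit.

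A patient who progresses would then be censored at, or soon after, progression. Progressed patients are at higher risk of death than those still under observation, so this censoring is informative. The Kaplan-Meier curve would mainly describe death before progression, or within a short window after it, and would lie above true OS. The reported median would be too long or would not be reached.

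**Working it through.** **Is there a plan figure to reproduce?** No. The documents give no expected number of deaths, median OS, OS power or length of survival follow-up. The check is therefore a reading of the text, then a conditional calculation.

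**Reading the sections together**

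| Section | What it implies for survival follow-up |
|---|---|
| 5.6, first sentence | Open: events to be tracked, or events that end follow-up |
| 5.6, second sentence | Scans stop at progression or death; silent on survival contact |
| 5.7 | On study until death, loss or withdrawal |
| 9.2, 10 | Progression described as leaving the study |
| 10, last column | Last scheduled contact 100 days after last dose |
| 11.1.6, 16.3 | No censoring of OS at progression, but censoring at last contact or last known alive |

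The sections conflict, and none sets a survival-contact interval.

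**Conditional size.** All inputs are assumptions: exponential times, median PFS 12 months, a share d = 10% of PFS events being deaths, median survival after progression 24 months, 36-month horizon. Then λ = ln 2/12 = 0.0578 and μ = ln 2/24 = 0.0289 per month. New therapy before progression is not modelled.

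*True OS.* S(t) = e^(−λt) + (1−d)·[λ/(λ−μ)]·(e^(−μt) − e^(−λt)), where (1−d)·λ/(λ−μ) = 0.9 × 2 = 1.8.
- S(24) = 0.25 + 1.8 × (0.50 − 0.25) = 0.70
- S(36) = 0.125 + 1.8 × (0.3536 − 0.125) = 0.536

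*Contact stops at progression.* Only deaths before progression are seen, so Kaplan-Meier estimates e^(−dλt).
- 24 months: e^(−0.1386) = 0.87, against 0.70
- 36 months: e^(−0.2079) = 0.81, against 0.54, or 28 points too high (0.812 − 0.536)
- Deaths captured by 36 months: d(1 − e^(−36λ))/(1 − S(36)) = 0.0875/0.464 = 19%

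*Contact lasts 100 days (L = 3.3 months) past progression.* For each progression-free patient at risk at time t ≥ L, there are R = (1−d)·λ·(e^((λ−μ)L) − 1)/(λ−μ) = 1.8 × (e^0.0953 − 1) = 0.18 progressed patients still observed. The observed hazard is (dλ + μR)/(1 + R) = (0.00578 + 0.00520)/1.18 = 0.0093 per month, and it is lower before L. Integrating to 36 months gives:
- Kaplan-Meier OS 0.72, against 0.54, or 18 points too high (0.720 − 0.536)
- Deaths captured: 34%

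*Range.* Over median PFS 8, 12 and 20 months, d = 5, 10 and 20%, and post-progression median 12 and 24 months (18 settings):

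| Contact | 36-month OS too high by | Deaths captured |
|---|---|---|
| Stops at progression | 12 to 58 points | 7 to 36% |
| 100 days past progression | 8 to 30 points | 25 to 49% |
| To death, loss or withdrawal (5.7) | No bias from this source | Those occurring by cut-off |

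*Shorter follow-up.* Section 17 asks for a final report within 12 months of the last patient's first visit, so 36 months for every patient is not the documented horizon. A simulation with cut-offs spread uniformly over 12 to 36 months (the same medians, d = 5 or 15%) gives about 7 to 19 deaths among 35 patients under full follow-up. The 24-month OS is 11 to 42 points too high if contact stops at progression (9 to 35% of deaths seen), and 7 to 21 points too high with 100 further days (34 to 52% seen).

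**The case against.** A reader might infer that 5.6 ends follow-up outright, that most deaths will never be observed, and that OS is therefore overstated. The documents do not support this as fact, for these reasons.

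- The first sentence of 5.6 does not say that follow-up ends at the earliest of the three events. The earliest-event wording is in the second sentence and governs scans only. Those scans continue past new therapy, which sits badly with reading new therapy as the end of follow-up.
- Section 5.7 keeps participants on study until death, loss or withdrawal, and neither 11.1.6 nor 16.3 censors OS at progression. Sites that act on 5.7 do not create this bias.
- The calendar is not a complete list. The 12-weekly scans that 5.6 requires after treatment have no column there either.
- The larger figures ignore the 100-day safety contact, which should find deaths in that window. The window runs from the last dose, and Section 5.5 allows treatment beyond RECIST progression, so contact could last longer than modelled and the bias could be smaller.
- No event rate comes from the documents.
- OS is descriptive, in a single-arm trial of up to 35 patients, with no comparator, power or decision rule.

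All of this stands, and it makes the bias conditional and lowers its priority. It does not close the gap. Section 5.7 says when a participant leaves the study, not how or when survival status is obtained. Loss to follow-up is itself an exit there, and is likelier where no contact is planned. The 100-day contact reduces the calculated bias but does not remove it.

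**Conclusion.** The plan conflicts with itself on how long participants are followed, and it leaves survival contact after the 100-day visit unspecified although OS is a stated endpoint. Whether OS is biased depends on which section sites follow. If they follow 5.6 and the calendar, the direction is upward and the size is material in every setting examined. The 8-to-30-point range is the more relevant one if the 100-day contact takes place; the 12-to-58-point range applies only if all contact stops at progression. Both rest on the assumed rates, exponential times and 36-month horizon. If sites track survival to death under 5.7, the bias does not arise, so it should not be stated as a certainty. The go/no-go decision in 16.2 uses response rate only and is unaffected. This should be fixed as a cheap improvement; it does not undermine the trial's main conclusion.

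**What to change.** Make three changes by amendment.

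1. In Section 5.6, state that vital status is collected at a fixed interval, for example every 12 weeks by telephone, chart or public record, regardless of progression or new therapy, until death, withdrawal, loss to follow-up or data cut-off. Keep the start of new therapy as a recorded date. The 12-week figure is a suggestion that matches the existing scan interval; what matters is that an interval is stated.
2. Reconcile 5.6 with 5.7, and reword the places in 9.2 and 10 that describe progression as leaving the study, so that leaving treatment and leaving the study are kept apart.
3. Add a survival follow-up column to the Section 10 calendar after the 100-day visit.

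The cost is the amendment wording and one short status check per patient per interval, with no added clinic visits, scans or patients.
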